## 1. VERSION HISTORY

**Table 1. Summary of Changes**

Version/ Date	Associated Protocol Amendment	Rationale	Specific Changes
1 11 August 2021	Original	N/A	N/A
2 03 May 2022	Original	Keeping consistency with study data and programming needs	
 
1. Removed the “years of education” in 3.4 since it is not relevant
 
2. Removed “The variables will be averaged over 20 mins of total activity.” in Section 3.1.1 in-lab activities data, as this data will be averaged per activity block (~7mins).
 
3. Removed “step length” in Section 3.1.1.1/2 and 3.2 to include only common endpoints across devices.
 
4. Remove “colored by sex” in 6.1 and 6.3.2 since gender is not relevant.
 
5. In table 5, refine the list of the physical activity metrics to better match what is used in DTS
 
6. Added “First and last day will be removed for this analysis as we do not expect whole 24 hours of data.” in 6.2.3 which is reasonable due to the nature of data collection.
 
7. Changed “90% CI” to “95% CI” for mixed effects models listed in 6.1, 6.2.6, and 6.3.2 to make it consistent with the general method.
 
8. Added the sentence that describes how to sum up in the individual wear comfort questionnaire in 6.2.4 as a clarification.
 

3 01 Sep 2023	Amendment 1 10 Apr 2023	Changes due to additional study cohort for addition of new device (Panaromic Bracelet, Cohort B)	
 
1. Incorporated study design, additional devices, and other changes according to Protocol Amendment 1 for Cohort B
 
2. Added objectives and endpoints for Cohort B
 
3. Added Statistical Analysis Methods for Cohort B
 

------------------	----------------------------	--	--

## 2. INTRODUCTION

This statistical analysis plan (SAP) provides the detailed methodology for summary and statistical analyses of the data collected in Study X9001263. This document may modify the plans outlined in the protocol; however, any major modifications of the primary endpoint definition or its analysis will also be reflected in a protocol amendment.

Text taken directly from the protocol is *italicized*.

*Assessing the appropriate levels of physical activity is a challenge in healthcare currently. Physical inactivity is linked to 10% of premature mortality and is the fourth leading cause of death globally. The benefit of physical activity in children is well defined: obesity prevention, reduction of cardiovascular risk factors, normal growth and development, depression prevention, reduction in risk of chronic diseases, health-related quality of life. The American guideline recommends 60 minutes per day of moderate-to-vigorous physical activity. However, there is a lack of standardized measures of gait and physical activity, and more accurate measures are needed.*

*There is a significant growth and interest in wearable accelerometry devices that can measure various gait and activity metrics. The ActiGraph device has been investigated in several studies involving children age from 2 to 18. Despite this growing interest, only a few studies have focused their objective on assessing the feasibility of implementing these types of devices. Also, little is known about how children and parents accept the devices and perceive their usability and comfort.*

*The rationale for this study is to compare gait quality metrics collected using the ActiGraph devices, APDM devices and GAITRite® walkway, during in-lab sessions (in the PfIRe Lab). APDM and GAITRite® walkway are used as reference comparators. GAITRite® is a pressure-sensitive walkway, which records gait metrics. APDM is a set of 6 devices that collect gait metrics. Both devices are used during in-lab assessments, but the deployment of these devices at home is impractical and not feasible. Hence the needed validation study of the ActiGraph device to measure for gait metrics continuously in a home environment.*

*In addition to the ActiGraph device studied in Cohort A, Cohort B of the study aims to evaluate the feasability of the Panaromic Bracelet and associated algorithms such as SleepPy and GaitPy compared to the GENEActiv device and to evaluate the comfort and wearability of the*

*Panoramic Bracelet. The results of this study will enable the use of novel devices in future clinical trials measuring scratch and sleep.*

*This study will generate compliance data and recruitment data to derisk future clinical protocols, and potentially enable the use of wearable devices in pediatric research studies. Device data from this study can be used for sample size estimates in future digital studies involving pediatric populations.*

## **2.1. Study Objectives**

### **2.1.1. COHORT A: ActiGraph Device**

#### **2.1.1.1. Primary Objective**

*To compare gait quality metrics collected using ActiGraph devices, APDM devices and GAITRite® walkway, during in-lab sessions.*

#### **2.1.1.2. Secondary Objectives**

- 1. To assess the feasibility of recruiting pediatric participants to conduct a wearable device study.*
- 2. To assess the ability of pediatric participants to perform a battery of lab-based tasks.*
- 3. To assess the compliance in wearing the ActiGraph devices at home.*
- 4. To evaluate the participant's or caregiver's perception of wearability and comfort of ActiGraph and APDM devices during in-lab sessions.*
- 5. To evaluate the participant's or caregiver's perception of wearability and comfort of ActiGraph devices during the at-home monitoring period.*
- 6. To evaluate the effect of floor surface (carpet vs. tile) on gait metrics collected using ActiGraph and APDM devices.*

#### **2.1.1.3. Exploratory Objectives**

- 1. To investigate the feasibility of using a daily activity diary to provide context in pediatric physical activity data collected by ActiGraph devices at home in pediatric participants.*
- 2. To compare gait speed collected using the SIMI® system and GAITRite® walkway, during in-lab sessions.*

### **2.1.2. COHORT B: Panoramic Bracelet Device**

#### **2.1.2.1. Primary Objective**

- 1. Evaluate the Panoramic Bracelet device and associated algorithms in the quantification of physical activity (eg sleep), scratch, and wear time, as compared to another accelerometry device (GENEActiv) during the at-home period.*

---

2. *To evaluate the participant's or caregiver's perception of wearability and comfort of Panoramic Bracelet device during the at home monitoring period.*

#### **2.1.2.2. Secondary Objectives**

1. *To assess the compliance in wearing the Panoramic Bracelet device at home.*
2. *To compare gait quality metrics collected using Panoramic Bracelet devices, APDM devices and GAITRite® walkway, during in-lab sessions.*

#### **2.1.2.3. Exploratory Objectives**

1. *To evaluate the participant's or caregiver's perception of wearability and comfort of Panoramic Bracelet device in-lab sessions.*
2. *To evaluate the effect of floor surface (carpet vs tile) on gait metrics collected using Panoramic Bracelet and APDM devices.*

### **2.2. Study Design**

*This is a non-randomized, single site, low-interventional study to compare gait quality metrics collected using the ActiGraph devices, APDM devices and GAITRite® walkway, during in-lab sessions (in the PfIRe Lab). There will be approximately 39 participants in Cohort A and 39 participants in Cohort B divided equally into 3 independent age groups based on the schematic detailed below:*

- *Group 1: 3 years to 5 years old inclusive;*
- *Group 2: 6 years to 11 years old inclusive;*
- *Group 3: 12 years to 17 years old inclusive.*

*Participant's assignment to a group will be determined by the age at the time the informed consent is signed. Participants will be recruited into age groups in parallel. Recruitment will stop in a group when there are at least 13 completers in that group. Participants who drop out for reasons other than safety before completion of the study may be replaced.*

*The study is composed of (see Figure 1):*

1. *A visit at the PfIRe Lab (Visit 1, Day 1), during which participant eligibility will be confirmed, consent and assent will be obtained. Participants will perform in-lab gait and activities monitoring procedures. During all these activities, participants will wear or interact with the following devices:*
  - a. *Wearable devices (ActiGraph for Cohort A), (Panoramic Bracelet device and GENEActiv for Cohort B);*
  - b. *GAITRite® Electronic Walkway;*

- c. *Ambulatory Parkinson's Disease Monitoring System (APDM);*
- d. *Camera based SIMI® system.*

*GAITRite® walkway, APDM will be used as reference comparators. For Cohort B of the protocol the aim is to use GENEActiv as a comparator device to Panoramic Bracelet during the at-home collection period. The in-lab gait and activity monitoring will be video recorded from multiple angles with multiple cameras (camera – based SIMI® system), this will be used to provide contextual information of each portion of the tasks and procedures that may be used by the reviewer when analyzing and interpreting the sensor data. As a tertiary/exploratory objective, gait speed recorded by the SIMI® system against the gait speed collected by GAITRite® walkway will be validated.*

The devices and activities in the study are listed in

Table 3 and

Table 3.

**Table 2. List of Devices Used in the Study**

Device	Information	Algorithms
GAITRite gait mat, model classic , 20ft	https://www.gaitrite.com/gait-analysis-walkways	GAITRite/PKMAS
APDM System, Version 2	https://www.apdm.com/wearable-sensors/	APDM
ActiGraph CentrePoint Insight Watch	https://www.actigraphcorp.com/cpiw/	ActiGraph, SKDH (gait, sit-2-stand, activity, sleep)
GENEActiv	https://activinsights.com/technology/geneactiv/	GENEActiv, SleepPy, ScratchPy, SKDH (wear, sleep, activity)
Panoramic Bracelet device	https://www.panoramicdigitalhealth.com/	SleepPy, ScratchPy, SKDH (wear, sleep, activity, gait)

**Table 3. Schedule of Activities and Devices Used in Each Activity**

[figure not shown]
Activity	Devices
Walk at natural speed	GAITRite, APDM (6 sensor-set), Actigraph Lumbar (Cohort A), Panoramic Bracelet (Cohort B)

Walk at slow and fast speed (self-paced)	GAITRite, APDM (6 sensor-set), Actigraph Lumbar (Cohort A), Panoramic Bracelet (Cohort B)
Walk on tile and carpet at natural speed	APDM (6 sensor-set), Actigraph Lumbar, Actigraph Wrist (Cohort A), Panoramic Bracelet (Cohort B)
In-lab Simulated Activities	APDM (6 sensor-set), Actigraph Lumbar, Actigraph Wrist (Cohort A), Panoramic Bracelet (Cohort B)
Free 10 minute walk (only Cohort B)	APDM (6 sensor-set), Panoramic Bracelet

[figure not shown]
2. *At-home monitoring for approximately 2 weeks (from Day 1 to Day 15 + 3 days) during which participants will wear the devices under the study. Complete a daily activity diary Day 2 to Day 15 (Only Cohort A). Complete activity and sleep diary for Cohort B on Day 2 to day 15.*
3. *Cohort B Only: At-home monitoring day 7+2 Wearability/comfort questionnaire for Panoramic Bracelet device and instruct participant to start wearing the GENEActiv device from Day 7 to end of study. Daily activity and sleep diary.*
4. *For Cohort A Only: A telephone follow-up interview at the end of the 2 weeks at-home monitoring period (Day 15 + 3 days) with administration of the Wearability/comfort questionnaire. For Cohort B follow up call to remind participants to take off devices and mail back. In addition to an end of study phone call for Cohort B.*

### Figure 1. Study Outline

#### Cohort A

#### Cohort B

\* The position of the GENEActiv device and the Panaromic Bracelet device closeness to the wrist (i.e., proximity of the device) will be balanced per age group. Approximately half the participants in each age group will wear the Panaromic Bracelet device proximal to the wrist and the GENEActiv device more distal to the wrist and vice versa

### 3. ENDPOINTS AND BASELINE VARIABLES: DEFINITIONS AND CONVENTIONS

#### 3.1. Primary Endpoints

##### Cohort A: Actigraph Device

This section contains a list of digital endpoints derived during in-lab activities related to the study primary objective in Cohort A: i.e., to compare gait quality metrics collected using ActiGraph devices, APDM devices and GAITRite® walkway, during in-lab sessions.

##### 3.1.1. In-Lab Activities

Each variable will be summarized as mean (or median depending on the distribution) over the activity duration. The in-lab simulated activities will last approximately 20 mins and be performed in two sets as detailed in the protocol (7 mins of activity, 5 mins of break, 7 mins of activity).

##### 3.1.1.1. Walk at Natural, Slow and Fast Speed Tasks:

##### GAITRite Walkway, APDM, Actigraph Lumbar:

- Double support (sec)
- Single limb support (sec)
- Stance time (sec)
- Swing time (sec)
- Stride length (meters)
- Step duration (sec)

- Cadence (steps/min)
- Gait speed (meters/sec)
- Steps (steps)
- Stride duration (sec)

The gait parameters for GAITRite and APDM will be derived from their manufacturer's algorithms (GAITRite and/or PKMAS, APDM: Mobility Lab). The gait parameters from the Actigraph sensor on the lumbar location will be derived by in-house built gaitPy algorithm^23.

### **3.1.1.2. In-lab Simulated Activities**

#### **APDM, Actigraph Lumbar:**

- Double support (sec)
- Single limb support (sec)
- Stance time (sec)
- Swing time (sec)
- Stride length (meters)
- Step duration (sec)
- Cadence (steps/min)
- Gait speed (meters/sec)
- Steps (steps)
- Stride duration (sec)

The gait parameters for APDM will be derived from the manufacturer's algorithm^22. The gait parameters from the Actigraph sensor on the lumbar location will be derived by in-house built gaitPy algorithm^23.

#### **Actigraph Wrist:**

- Total number of steps (#)

The number of steps will be derived from the manufacturer's default algorithm^24. We will extract the total number of steps over the activity periods in the epoch data file.

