- f. Varied speeds include participant's self-chosen slow pace ("Walk slow") and fast pace ("Walk fast").
- g. Participant will alternate between activities' stations. Participants will do ~7 minutes of activities, ~5 minutes of break and ~7 minutes of activities. The task stations include 2 sitting activities, 2 standing activities, and 2 walking activities. Order of stations will be determined at random using dice roll.
- h. Participants will complete activity diary (choice between either electronic or paper) at home daily between Day 2 and Day 15.
- i. The study staff will instruct the participants to mail back both ActiGraph devices at the final study evaluation over the phone at the exit interview.
- j. Any event with a device (issues with devices, loss of the devices, etc.), the impact of this event and the action taken with device will be recorded in a device assessment CRF.
- k. Adverse events (AEs) will be queried at the clinic visit and during the exit phone interview using open-ended and nonleading verbal questioning of the participant. Any spontaneously reported AEs noted during the home visits will be captured during the exit phone interview.

Abbreviations: → = ongoing/continuous event; APDM = Ambulatory Parkinson's Disease Monitoring.

COHORT B: PANORAMIC BRACELET SoA

Procedure/ Assessment	In-Lab		At-home monitoring															Final study evaluation	Return of Study Materials
	Screening	Visit 1	Day 1	Day 2	Day 3	Day 4	Day 5	Day 6	Visit 2	Day 8	Day 9	Day 10	Day 11	Day 12	Day 13	Day 14	Day 15		
	Day 1	Day 1							Day 7 +2									Day 15 (+3 days)	> Day 15
Informed Consent and Assent	X																		
Demography	X																		
Medical/Surgical History ^a	X																		
Prior/Concomitant treatment ^a	X																		
Inclusion/Exclusion criteria	X																		
Height, leg length ^b and weight		X																	
Edinburgh Handedness Inventory (EHI)-short form		X																	
Device exposure (APDM provisioning) ^c		X																	
Device exposure (In-Lab Panoramic Bracelet Device provisioning) ^d		X																	
Walking on GAITRite® walkway (~20 feet x 3) at participant's natural speed ^e		X																	

PFIZER CONFIDENTIAL

CT45-GSOP-RF15 2.0 Low-Interventional Study Protocol Template 05-Dec-2019

Page 29 of 76

Procedure/ Assessment	In-Lab		At-home monitoring															Final study evaluation	Return of Study Materials

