Walking on GAITRite® walkway (20 feet x 3) at participant's natural speed and at various speed	
• Compare gait metrics collected between devices and APDM devices.• Compare gait metrics collected between devices and GAITRite® walkway.• Compare gait speed collected between SIMI system and GAITRite® walkway.	GAITRite® walkway
Walking on tile and carpet at participant's natural speed	
• Compare gait metrics collected between devices and APDM devices.	Tile and Carpet
Moving naturally between activities' stations	
• Compare gait metrics between devices and APDM devices, collected during the walk between the activities' stations and during the sit/stand position at the stations.	Walking pathway between activities' stations

Table 1. In-lab Assessments

Assessments	Objectives	Location
Free 10 minute walk (Cohort B)	
Compare gait metrics between devices and APDM devices, collected during the walk	10 minute walk outside the lab

1. At-home monitoring for approximately 2 weeks (from Day 1 to Day 15 + 3 days) during which participants will wear the devices under study. Complete a [daily activity diary](#) on Day 2 to Day 15 (Only Cohort A). Complete activity and sleep diary for Cohort B on Day 2 to day 15.
2. Cohort B Only: At-home monitoring day 7+2 Wearability/comfort questionnaire ([Annex 5](#)) for Panoramic Bracelet device and instruct participant to start wearing the GENEActiv device from Day 7 to end of study. Daily activity and sleep diary. ([Annex 8](#))
3. For Cohort A Only: A telephone follow-up interview at the end of the 2 weeks at-home monitoring period (Day 15 + 3 days) with administration of the [Wearability/comfort questionnaire \(Annex 5\)](#). For Cohort B follow up call to remind participants to take off devices and mail back. In addition to an end of study phone call for Cohort B.

For a detailed description of the study activities, see [Section 6 Schedule of Activities](#).

Inclusion Criteria

Participants must meet all of the following inclusion criteria to be eligible for inclusion in the study:

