10. Move naturally (sit/stand/walk) through a random path created by dice roll in the PflRe Lab (between activities' stations) while wearing device under study and APDM system as well as recorded with video/motion capture cameras. Participants will perform age-related activities using 6 activity stations for ~20 minutes (defined as follows: ~7 minutes of activities, ~5 minutes of break and ~7 minutes of activities). The task stations include 2 sitting activities (such as look through a book, draw/write), 2 standing activities (such as turn a switch or hang a coat), 2 walking activities (such as move blocks/objects, toss a beanbag and pick it up).
11. Free 10 minute walk outside the lab (Cohort B Only)
12. [Wearability/Comfort questionnaire \(Annex 5\)](#) followed by a [Cognitive Debrief](#) of the questionnaire.
13. Instruct participant and parent(s)/LAR on use of device under study and activity diary (Cohort A only) and activity and sleep diary (Cohort B only) at home.
14. Monitor for AEs.

[figure not shown]
A medically qualified individual is responsible for reviewing the inclusion/exclusion criteria, medical/surgical history, prior/concomitant treatments and for the review of the systems.

For the assessments 8, 9 and 10, every participant will have up to 3 attempts.

The in-lab gait and activity monitoring will be video recorded from multiple angles with multiple cameras (camera-based SIMI system). This will be used to provide gait speed and contextual information of each portion of the tasks and procedures that may be used by the reviewer when analyzing and interpreting the sensor data. Time segments of sensor data from each modality will be identified based on these annotations.

The locations of the device under study and the APDM system on the participant's body are defined on [Figure 1](#).

Figure 1. Wearable Sensor Device Locations on Participant In-lab Cohort A and B

Legend:

- Blue circle – APDM Opal sensors to be worn on each wrist, chest, lumbar, and above each shoe.
- Orange triangle – Device under study to be worn on nondominant wrist and lumbar.

All in-lab assessments will be performed at the PflRe lab with site personnel and will take approximately 2 hours.

Any event with a device, the impact of this event and the action taken with device will be recorded in a device assessment CRF during Visit 1.

At-home Monitoring (Day 1 to Day 15+3 days)

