**Table 8. Specific Endpoints and Analyses for Primary Objective (Cohort A)**

Task	Devices	Measurements/comparisons
In-lab walk at natural speed	Reference: GAITRite, APDM (Mobility Lab) Comparator: Actigraph Lumbar (gaitPy)	Common gait metrics* (Comparison across devices)
In-lab walk at slow and fast speed (self-paced)	Reference: GAITRite, APDM (Mobility Lab), Comparator: Actigraph Lumbar (gaitPy)	Common gait metrics* (Comparison across devices)
In-lab Simulated Activities	Reference: APDM (free living method) Comparator: Actigraph Lumbar (gaitPy)	Common gait metrics* (Comparison across devices)
In-lab Simulated Activities	Reference: APDM (free living method) Comparator: Actigraph Wrist, Actigraph Lumbar (gaitPy)	Number of Steps (Comparison across devices)

\* Common gait metrics between devices are Double Support Time, Single Limb Support Time, Stance Time, Swing Time, Step Duration, Stride Duration, Stride Length, Gait Speed, and Cadence, as in Section 3.1.1.1 and 3.1.1.2.

Appropriate summaries and plots for each digital endpoint will be produced **per task** (colored by age group, if necessary) as follows:

- Scatter plots of digital metrics from each reference device vs comparator device with corresponding regression line and 95% confidence interval (CI) will be plotted.
- Accuracy of the sensor-derived metrics will be determined by computing the mean difference, mean absolute difference, variation of the difference, the mean percent error, the mean absolute percent error and the effect size between reference device(s) and comparator device metrics.
- Bias will be assessed by Bland-Altman plots and 95% limits of agreement between each reference devices and comparator device. Specifically, the following error measures will be computed: mean difference, lower and upper 95% limit of agreement.
- Intra-class correlation coefficient (ICC) and its lower and upper confidence limits between metrics derived from reference devices and comparator device will be computed.
- For in-lab walk at natural, slow and fast speed tasks, the ICC will be used to compare gait endpoints derived from APDM, GAITRite and Actigraph lumbar sensor.
- The correlation coefficients (Pearson's) between metrics from each reference device and comparator device will be calculated.
- Box and whisker plots of digital metrics from each reference device and comparator device will be plotted.

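### The wrist step count is compared with APDM as a total over mixed sitting, standing and walking stations, so opposite errors can offset, and the sit/stand comparison in Protocol Table 1 has no analysis

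*SAP*

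**What the plan says.** SAP 3.1.1.2 takes the wrist step count from the manufacturer's algorithm: "We will extract the total number of steps over the activity periods in the epoch data file". Table 8 gives it a single row for the simulated activities, "Number of Steps (Comparison across devices", with APDM as reference and the ActiGraph wrist and lumbar counts as comparators. SAP 6.1 produces its agreement outputs per task.

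The task is mixed by design. Footnote g of the protocol's Schedule of Activities states: "The task stations include 2 sitting activities, 2 standing activities, and 2 walking activities". Station order is set by dice roll. The examples under Visit 1 (Day 1) are largely hand tasks: drawing or writing, turning a switch, hanging a coat, moving objects, tossing a beanbag.

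No SAP section divides the count by posture. SAP 3.1.1 sets the general unit for in-lab variables: "Each variable will be summarized as mean (or median depending on the distribution) over the activity duration". The finest unit named is in the SAP version history: "this data will be averaged per activity block (~7mins"), and a block of that length still contains several stations.

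Protocol Table 1 says that this task compares the devices with APDM while the child walks from station to station and also "during the sit/stand position at the stations". The protocol's Statistical Analysis section for the Cohort A primary objective mentions only the natural walk for this task. The SAP has no sit/stand comparison either.

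**The concern.** A wrist counter may go wrong in two ways here. It may register arm movement as steps while the child sits or stands, and it may miss steps while the child walks with occupied hands. In a total, these errors enter with opposite signs. A small mean difference could then come from an accurate counter or from two sizeable errors that happen to balance, and no planned statistic tells these apart. The balance also depends on the station mix the lab chose.

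This comparison is part of the Cohort A primary objective. What is at stake is what the wrist row of Table 8 can conclude. In addition, a comparison named in one part of the protocol has no analysis anywhere.

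**Working it through.** **The plan's own figure.** The documents give no expected step count, miss rate or false-step rate, so there is nothing of the plan's to reproduce for steps. The Cohort A sample size rests on gait speed, and it reproduces. With two measurements per child, k = 1 + 4(z_alpha + z_beta)² / (ln C)², where C = (1 + 2×0.27/0.73) / (1 + 2×0.72/0.28) = 1.740/6.143 = 0.283. With one-tailed alpha 0.05 and power 0.80, k = 1 + 4×6.183/1.592 = 16.54, so 17. This point does not affect it.

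**Identity.** With APDM taken as correct, error in the total = extra steps outside walking − steps missed while walking.

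**Break-even rate.** Let s be the share of activity time spent walking, c the cadence and m the fraction of walking steps missed. Extra steps per minute outside walking that fully offset the misses:

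f = m × s × c / (1 − s)

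Activity time is about 7 + 7 = 14 minutes (Schedule of Activities). The rest is assumed: s = 1/3 and c = 110 steps/min.

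- True steps: 14 × 1/3 × 110 = 513. Time outside walking: 14 × 2/3 = 9.33 min.
- m = 10%: 51.3 / 9.33 = 5.5 extra steps/min.
- m = 20%: 102.7 / 9.33 = 11.
- m = 30%: 154 / 9.33 = 16.5.
- Range for m = 10%, with s from 0.2 to 0.5 and c from 90 to 130: from 0.1×0.2×90/0.8 = 2.25 to 0.1×0.5×130/0.5 = 13.

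**Effect on the planned statistics.** Simulation of 39 children, 2,000 runs, with the SAP's ICC form (two-way random effects, absolute agreement). Assumed spread between children: s has SD 0.07, c has SD 12, and the miss and extra-step rates each have SD 30% of their mean. The total also carries counting noise of SD 10 steps. The walking-only figures carry none, which slightly favours them.

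| Missed | Extra/min | Total: bias | Total: limits of agreement | Total: MAPE | Total: ICC | Walking: bias | Walking: MAPE | Walking: ICC |
|---|---|---|---|---|---|---|---|---|
| 10% | 5.5 | 0 | −58 to 58 | 5.0% | 0.97 | −51 | 10% | 0.89 |
| 20% | 11 | 0 | −110 to 110 | 9.4% | 0.87 | −103 | 20% | 0.66 |
| 30% | 16.5 | 0 | −165 to 165 | 14.1% | 0.70 | −154 | 30% | 0.43 |
| 20% | 0 | −103 | −182 to −23 | 20.0% | 0.65 | −103 | 20% | 0.66 |
| 0% | 11 | 103 | 36 to 169 | 21.8% | 0.70 | 0 | 0% | 1.00 |

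Rows 2, 4 and 5 belong together. Either error alone gives a clear bias and an ICC of 0.65 or 0.70, which the SAP 5.1 benchmarks call good. Both together give zero bias and 0.87, which they call excellent.

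The offset is not invisible. In row 2 the limits are ±110/513 = ±21% of true steps and MAPE is 9.4%. These show that something is wrong, but not whether it arises in walking or outside it.

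**The case against.** Several objections have force.

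- **The error rates and their signs are assumed.** The documents do not show how the wrist algorithm behaves. Tossing a beanbag could add counts at a walking station. This stands: the errors can offset, but nothing shows that they do.
- **Not every statistic is masked.** A reader might infer that mean difference, MAPE, limits of agreement and ICC could all look near perfect. That needs exact offset within every child. With ordinary variation between children, only the mean bias vanishes. The ICC is raised, and MAPE and the limits keep part of the error.
- **The sit/stand comparison is not a formal endpoint.** A reader might infer that the SAP dropped a false-step question posed by the protocol. The documents do not support this. The phrase is in Table 1 only and concerns gait metrics, the wrist step count is in neither Annex 2 nor Annex 3, and the protocol's own analysis text already omits sit/stand. The inconsistency starts within the protocol. Still, most gait metrics have no meaning in a seated child, so step count is the listed measure that could answer the Table 1 item.
- **Transfer to the home is not at issue in the planned analyses.** The protocol's rationale looks to gait measurement at home, but SAP section 6 plans no at-home analysis of steps. The wrist measures in SAP Table 6 are activity times, calories, counts and vector magnitude.
- **The total may be two block totals, or may already be cut by annotation.** A block still mixes stations. The protocol does say "Time segments of sensor data from each modality will be identified based on these annotations", but the SAP does not say that this governs step extraction. If it does, one sentence would settle it.
- **The lumbar count is less exposed.** The protocol has GaitPy's feature algorithm work on pre-identified gait bouts. If that limits the lumbar count, few steps outside walking enter it, and the wrist and lumbar counts in the same Table 8 row are not like for like.

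**Conclusion.** The point holds in a limited form. The Table 8 step comparison cannot separate a counter that is accurate from one whose errors outside walking offset its errors in walking. Mean bias can be hidden completely and the ICC can move up a benchmark category, as from 0.66 for walking alone to 0.87 for the total in the 20% case. MAPE and the limits of agreement would reveal part of the error without locating it. These sizes rest on assumed rates, an assumed walking share and cadence, and APDM taken as truth; the real size is unknown. Separately, Protocol Table 1 and the protocol's Statistical Analysis section disagree on whether a sit/stand comparison is made, and must be reconciled. This is a modest, inexpensive improvement to one row of the primary analysis.

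**What to change.** In SAP 3.1.1.2 and the Number of Steps row of Table 8:

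- Define the activity periods, including whether they are one total or two block totals.
- Using the planned video-annotated segments, report the wrist count separately for walking segments (net difference and percent error against APDM) and for sit/stand segments (device steps per minute, with APDM alongside). Keep the total as an overall result.
- Treat the lumbar count the same way where GaitPy yields steps outside pre-identified gait bouts; otherwise state that it does not.
- Use the shortest wrist epoch available and state its length, since it limits how cleanly segments can be cut.
- Do not call the walking-segment figure the percent of steps missed. It is still net of missed and extra steps, and separating those would need step-level matching or a video step count, neither of which is planned.

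In the protocol, either carry the Table 1 sit/stand comparison into the analysis text or state that it is not made.

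The cost is posture labelling of segments, extra programming, and shorter segments with fewer steps in each. No new procedure is needed and the sample size is unchanged. Cohort A data collection was planned to end on 01 April 2022 and its interim report was planned for 01 March 2023, both before SAP version 3 (01 September 2023). On those dates the split would be a post hoc re-analysis for Cohort A and should be labelled so.
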